### *The short questionnaire to assess health-enhancing physical activity (SQUASH)*

SQUASH is used to measure physical activity. Based on the reported effort, the intensity of the activities is assigned an intensity score. The reported sports activities are given a MET value based on Ainsworth's compendium of Physical Activities, and the intensity score is adjusted according to reported effort. Activities are divided into three intensity categories: (1, light) 2 to < 4 MET, (2, moderate) 4 to < 6.5 MET, and (3, vigorous) ≥ 6.5 MET, and the time per week spent in each category is calculated. The activity score for each item is calculated by multiplying the intensity score and time per week. The total activity score is calculated as the sum of activity scores. Activities with intensity lower than 2 MET will not be included as they are considered to contribute negligibly to physical activity level.

### *Tampa Scale of Kinesiophobia 17 items (TSK-17)*

The Tampa Scale of Kinesiophobia (TSK) is a valid and reliable tool to assess somatic focus and activity avoidance in patients. TSK-17 consists of 17 statements that measure pain-related fear of movement in patients with chronic musculoskeletal pain. Each

statement is provided with a 4-point Likert scale, and total scores range from 17 to 68, with a higher score indicating more fear of movement.

### **Health Economic Evaluation:**

We will conduct a cost-effectiveness and cost-utility analysis comparing the physiotherapist-led strength exercise intervention to usual care and estimating the incremental costs per unit of health outcome gained. The health outcomes will be health-related QoL measured using the EQ-5D-5L and iHOT-33. Costs will be measured using the Health care utilization questionnaire (HUQ) and the Productivity Costs Questionnaire (iPCQ).

#### *EuroQol 5-dimension 5-Level (EQ-5D-5L) and EQ-VAS*

Health-related QoL will be assessed using the reliable and valid EuroQol Group 5-dimension 5 Level instrument (EQ-5D-5L), including the summary index ranging from -0.624 (worst) to 1 (best) (Danish value set). The EQ-5D-5L is a generic instrument for describing and valuing health. It is based on a descriptive system that defines health in terms of 5 dimensions: Mobility, Self-care, Usual activities, Pain/discomfort, and Anxiety/depression. Each dimension has 5 response categories corresponding to no problems, slight problems, moderate problems, severe problems, and extreme problems. The instrument is designed for self-completion, and respondents also rate their overall health on a vertical visual analog scale (EQ-VAS) ranging from 0 (worst imaginable health) to 100 (best imaginable health). The EQ-5D-5L and EQ-VAS have been widely tested and used in both the general population and patient samples.

#### *Healthcare utilization questionnaire (HUQ):*

Healthcare utilization and medication usage are measured by a nine-item patient-reported cost questionnaire (HUQ) including visits to primary care physician and therapist, medical specialist, outpatient hospital care, hospital admissions, diagnostic tests, and medical procedures.

#### *The Productivity Costs Questionnaire (iPCQ):*

The Productivity Cost Questionnaire (iPCQ) includes three modules measuring productivity losses due to 1) absenteeism, 2) presenteeism of paid work, and 3)

productivity losses related to unpaid work. The iPCQ consists of 18 questions. Productivity losses are measured in three separate modules, allowing the option of leaving out specific types of productivity losses when these are not relevant for a specific patient.

## **Analysis methods**

### **Primary analysis**

#### *Intention-to-treat analysis:*

The primary analysis of clinical effectiveness will be the assessment of the between-group mean difference in change in hip-related QoL (iHOT-33) from baseline to 6 months after randomization. Between-group mean differences in change larger than 6.1 points will be considered clinically relevant. Consequently, to determine the intervention's effectiveness compared to usual care, the lower limit of the 95% confidence interval for the mean difference must be greater than 6.1 points. Secondary analysis will be the assessment of the between-group mean difference in change in secondary outcomes from baseline to 3 months, 6 months, and 12 months. Assessment of between-group differences in changes will be conducted using a linear mixed-effect model for continuous variables and a generalized linear mixed-effect model for binary variables. This approach accounts for the correlation between repeated measurements within the same patient over time. The model will include fixed effects for the intervention group (physiotherapist-led exercise or usual care) and time points (Baseline, 3, 6, and 12 months). Patients and recruitment sites (Aarhus, Aalborg, Hvidovre, Horsens, or Melbourne) will be included as random effects to account for potential clustering effects. To assess whether the effect of the intervention on hip-related QoL (iHOT-33) varies over time, an interaction term between the intervention group and time will be included. Supplementary, to further guide the clinical interpretation of change in iHOT-33, the between-group difference in the proportion of participants achieving the minimal clinically important difference of 6.1 for within-patient score change was analyzed using an a-priori threshold of 20%. A difference of less than 20% was considered no meaningful difference between treatments, and 20% or greater was considered a meaningful difference. A sensitivity analysis for thresholds of 10% and 30% will be conducted. Supplementary to this interpretation, we will conduct calculations for other identified values of minimal important change by Scholes et al., of 8.7 points, and Kemp et al., of 10.0 points.

The primary analysis and subsequent inferences will follow the intention-to-treat principle, which means that all participants will be analyzed in the groups to which they were originally randomized, regardless of their adherence to the assigned treatment.

Model validation will be performed by comparing observed and expected within-subject standard deviations and correlations and by inspecting plots of standardized residuals versus fitted values and QQ plots for the standardized residuals.

*Per protocol analysis:*

Supplementary to the intention-to-treat analysis a per protocol analysis will be conducted. This analysis will focus on participants who strictly adhere (i.e., > 75 % total number of sessions) to the assigned treatment protocol. It will provide additional insights into the treatment effect among participants who complied with the assigned intervention. Furthermore, a sub-analysis will exclude patients who have received hip surgery within 6 months of follow-up.

*Missing data*

No imputations will be applied in the primary analysis. Each randomized participant will be included in the intention-to-treat analysis with the data collected for the participant. An attempt to collect data from all randomized participants will be made, regardless of adherence to interventions.

*Outliers*

The dataset will be visually inspected and examined to identify outliers potentially caused by typographical errors. These outliers will be cross-referenced with other data sources (e.g., printed test schemes) or through discussion with the responsible outcome assessor. If confirmed, these outliers will be corrected to actual values. Alternatively, outliers will be removed from the dataset if there is confidence that they are data errors. A sensitivity analysis will be conducted to assess the impact of outlier handling decisions on the statistical analysis results. If the conclusions change substantially due to the exclusion of potential erroneous measurements (which are not confirmed), both conclusions will be reported; otherwise, only the conclusion from the analysis, including all data, will be presented.

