## **Timing of outcome assessments**

Outcome assessments are planned at baseline and 6 months follow-up for performance-based physical functioning tests (e.g., maximal muscle strength in the one-repetition maximum unilateral leg press, single leg jump for distance, and one leg rise test). Outcome assessments are planned at baseline, 3, 6, and 12-month follow-ups for patient-reported outcome measures and cost. See Table 1 in the study protocol.

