## **STATISTICAL PRINCIPLES**

### **Confidence intervals and p-values**

Results will be expressed as between-group differences in means with 95% confidence intervals.

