#### *Patient Acceptable Symptom State (PASS)*

PASS is defined as the value beyond which patients consider themselves well, and will be assessed using a single question.

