**Pain Kinesiophobia**

TSK-17 (17-68), mean (SD)

FAI: Femoroacetabular Impingement. NSAID: Nonsteroidal Anti-inflammatory Drugs. MET: Metabolic Equivalent.

SQUASH: the short questionnaire to assess health-enhancing physical activity. TSK-17: Tampa Scale of Kinesiophobia.

SD: Standard Deviation. 95% CI: 95% Confidence Interval. MET: Metabolic Equivalent.

If data is not normally distributed median and interquartile range (IQR) will be reported instead of the mean and standard deviation (SD).

**Table 2:** Changes from baseline to 6-month follow-up in primary and secondary outcomes in the intention-to-treat-population.

	Physiotherapist-led exercise (n = )			Usual care (n = )			Difference in change (95% CI)	
	Baseline (95% CI)	6-mo (95% CI)	Change (95% CI)	Baseline (95% CI)	6-mo (95% CI)	Change (95% CI)		
Primary								
iHOT-33, (0-100)								
Secondary								
1-RM Leg Press, Kg								
Index hip								
Non-index hip								
Hop for Distance, cm								
Index hip								
Non-index hip								
One-Leg Rise Test, Reps								
Index hip								
Non-index hip								
PASS (% Yes)								
GPE QoL								
GPE Pain								
GPE ADL								
Hip surgery (%)								

6-mo: 6-month follow-up. 95% CI: 95% Confidence Interval. iHOT-33: International Hip and Outcome Tool 33. 1 RM: 1 Repetition Maximum. Reps: Number of repetitions (0-50). PASS: Patient Acceptable Symptom State. GPE: Global Perceived Effect. QoL: Quality of Life.

**Table 3:** Changes from baseline to 6-month follow-up in the other outcomes in the intention-to-treat-population.

	Physiotherapist-led exercise (n = )			Usual care (n = )			Difference in change (95% CI)
	Baseline (95% CI)	6-mo (95% CI)	Change (95% CI)	Baseline (95% CI)	6-mo (95% CI)	Change (95% CI)	
iHOT-33 subscales, (0-100)							
Symptoms							
Sport							
Job							
Social							
HAGOS subscales, (0-100)							
Pain							
Sport							
Quality of Life							
SQUASH							
Total activity score (MET)							
Light intensity (min/week)							
Moderate intensity (min/week)							
Vigorous intensity (min/week)							
Sport participation							
HSAS, (1-8)							
RTS, (1-4)							

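### PASS is analysed as change from baseline in a generalized mixed model with no stated link or effect measure, while Table 2 reports percentage points; the two scales can disagree in size and even sign

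*SAP*

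**What the plan says.** The Intention-to-treat analysis section of the SAP defines the secondary analysis as the "between-group mean difference in change in secondary outcomes from baseline to 3 months, 6 months, and 12 months". The method is "a linear mixed-effect model for continuous variables and a generalized linear mixed-effect model for binary variables". The fixed effects are group and "time points (Baseline, 3, 6, and 12 months", so baseline is a response level and not a covariate. The section adds that "an interaction term between the intervention group and time will be included", but gives the reason for this in terms of iHOT-33 only.

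PASS is listed as a secondary outcome that "will be assessed using a single question". On timing, the SAP says: "Outcome assessments are planned at baseline, 3, 6, and 12-month follow-ups for patient-reported outcome measures and cost". Table 2 shows PASS as the percentage answering yes, under columns for baseline, 6 months and change in each arm and a final column headed "Difference in change (95% CI".

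The general reporting rule, under Confidence intervals and p-values, is: "Results will be expressed as between-group differences in means with 95% confidence intervals". The SAP names no link function, no effect measure for binary outcomes, and no step from the model's scale to percentages.

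**The concern.** For a continuous outcome, the group-by-time coefficient of a linear mixed model is the difference in mean change, so model and table agree. For a binary outcome this holds only with an identity link, or if fitted probabilities are averaged and then subtracted. With a logit link the coefficient is the log of a ratio of odds ratios, conditional on the patient's random effect. That is a different quantity from the one Table 2 shows.

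Two consequences follow. First, two analysts who both follow the SAP could report different PASS results from the same data, and the choice of scale could be made after seeing them. Second, randomisation makes the true baseline difference zero, so subtracting the observed one adds chance variation. How much it adds depends on the scale. On the logit scale a rare baseline yes is very imprecise; on the percentage scale it has little variance.

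**Working it through.** The SAP gives no figure for PASS, so there is none to reproduce.

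**Inputs.** 60 per arm is from the sample size section. Everything else is assumed: logit link, 50% yes at 6 months, within-patient correlation (phi) of 0.2 between baseline and 6 months, and a baseline yes rate p0 of 20%, 10% or 5%.

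**1. The two scales can disagree.** Suppose 60 per arm, exercise going from 6 to 36 yes and usual care from 2 to 20.
- Percentage points: (36 − 6)/60 − (20 − 2)/60 = 50% − 30% = +20 points for exercise.
- Exercise odds ratio, 6 months to baseline: (36/24)/(6/54) = 13.5. Usual care: (20/40)/(2/58) = 14.5. Ratio: 13.5/14.5 = 0.93, on the other side of no effect.
- 6-month comparison alone: 60% against 33.3%, which is 26.7 points, with odds ratio 1.5/0.5 = 3.0.

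A second case: 5% to 45% against 10% to 50%. The difference in change is 0 points, but the ratio of odds ratios is (0.818/0.0526)/(1/0.111) = 1.73.

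These are ratios of observed odds. A mixed model gives patient-specific ratios, which will differ in size.

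**2. Precision on the logit scale.** V0 = 2/(60 p0(1 − p0)); V6 = 2/(60 × 0.25) = 0.133, so the SE of the 6-month comparison is 0.365. The SE of the difference in change is sqrt(V0 + V6 − 2 × 0.2 × sqrt(V0 V6)).

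**3. Precision on the percentage-point scale.** Same formula, with V0 = 2 p0(1 − p0)/60 and V6 = 2 × 0.25/60 = 0.00833.

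| Baseline yes | SE of change, logit | Ratio to 6-month SE, logit | Ratio to 6-month SE, percentage points |
|---|---|---|---|
| 20% | 0.52 | 1.44 | 1.15 |
| 10% | 0.64 | 1.76 | 1.06 |
| 5% | 0.84 | 2.31 | 1.01 |

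The number per arm cancels from the ratios, so dropout that is equal at both visits does not change them.

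**4. Estimability.** The chance that at least one arm has no baseline yes is 1 − (1 − (1 − p0)^60)^2: 0.4% at 10%, 9% at 5% and 51% at 2%. The logit contrast then has no finite estimate.

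**5. Check against a fitted mixed model.** A logistic random-intercept model with group, four visits and their interaction was simulated with 60 per arm, 6-month PASS of 30% against 50%, and patient SD of 1 and 2. At 5% baseline yes, power was 13–16% for the logit change contrast and 56–66% for the model's 6-month contrast. The share of the logit change variance due to baseline was 69–79% at 5% baseline yes, 56–65% at 10%, 35–51% at 20% and 23–42% at 30%. The two scales gave opposite signs in about 11–12% of fitted trials at 5%, 6–7% at 10% and 2–3% at 20%. By approximation on the percentage-point scale, ignoring within-patient correlation, power at 5% baseline yes was 55% with baseline subtracted and 63% without.

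**The case against.** A reader might infer that the SAP commits PASS to an analysis far less precise than the data allow, dominated by baseline noise. The document does not support that.

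- The large SE ratios apply only if inference is taken from a logit interaction, and the SAP names neither a logit link nor a ratio of odds ratios. On the scale of Table 2 the loss is 1% to 15% in SE, and a rare baseline yes is nearly harmless.
- No baseline PASS rate is given. Eligibility requires pain for at least 3 months but sets no severity threshold, so a low rate is plausible, not established. In the simulation, baseline noise is the larger part of the logit variance at about 10% or below and a minority at 30%.

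Nor is the mixture of scales a contradiction. A generalized mixed model can yield marginal probabilities and their difference. That step is unstated, not excluded.

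The worked examples use chosen baseline imbalances. In the first, ignoring within-patient correlation, the SE of the log ratio is sqrt(1/6 + 1/54 + 1/36 + 1/24 + 1/2 + 1/58 + 1/20 + 1/40) = 0.92. The 95% interval around 0.93 therefore runs from about 0.15 to 5.7. This shows an uninformative contrast, not evidence against exercise.

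Table 2 is also a general shell. It gives the same columns to global perceived effect, which is already a rating of change, and to hip surgery, so its baseline column alone is weak evidence that baseline PASS is modelled.

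All of this limits the size of the point. What remains is that the text, not only the table, sets difference in change as the secondary contrast, includes baseline as a time point, and schedules patient-reported outcomes at baseline. The effect measure is still open.

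A last objection is that modelling follow-up visits alone drops participants with no follow-up PASS. They carry almost no information on the treatment contrast, and constraining baseline equal between arms keeps them.

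**Conclusion.** The point holds as a specification gap with a conditional cost. The SAP sets a change-from-baseline contrast for a binary outcome in a model whose scale it does not name, and reports it in percentage points without saying how to get there. With a logit link, the two quantities can differ in size and sign. If the logit contrast is used for inference, its SE is about 1.4 to 2.3 times that of the plain 6-month comparison for baseline yes of 20% down to 5%, and it may not be estimable at very low rates. On the percentage-point scale the ratio is about 1.15 to 1.01.

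These figures rest on 60 per arm, 50% yes at 6 months, a correlation of 0.2 and an assumed baseline rate. PASS is one secondary outcome with no success criterion attached, and the primary iHOT-33 analysis is unaffected. It should be corrected before analysis because the repair is cheap and removes a choice of scale that could otherwise be made after seeing the data.

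**What to change.** In the Intention-to-treat analysis section, add a short paragraph for PASS:

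- State the link function. Do not subtract baseline.
- Estimate the between-group difference in proportions at each follow-up (6 months for Table 2) from the mixed model by marginal standardisation, averaging over the random effects, with a 95% CI.
- Enter baseline PASS as a covariate in a model of the follow-up visits. Alternatively, keep baseline as a response level constrained equal between arms, so that every randomised participant with any PASS answer contributes. Choose one of the two in advance.
- State that the group-by-visit term also applies to PASS.

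In Table 2, replace the change and difference-in-change cells of the PASS row by the 6-month proportions and their difference with a 95% CI. The baseline percentages can stay as description.

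The cost is a few sentences and one table row, with no new data and no change to the primary analysis.

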## **STUDY METHODS**

### **Trial design**

The Better Hip trial is a multicenter, stratified (by hospital site), randomized (allocation 1:1), controlled, parallel-group, assessor-blinded, superiority trial conducted in Denmark (Aarhus, Horsens, Hvidovre, Aalborg, and Odense) and Australia (Melbourne).

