### **Sample size calculation**

The sample size calculation is based on a clinical superiority calculation using data from a pilot RCT by Kemp et al. Kemp et al. found a mean change of 27 (SD 26) points on the iHOT-33 in their strength exercise group (e.g., intervention group) and a mean change of 11 (SD 8) points in their stretching group (e.g., control group) after 12 weeks of intervention (between-group difference of 16 [95% CI -9; 38] points). The superiority margin is a 6 points MCID in the between-group change on the iHOT-33. The estimated mean difference of 16 points, a superiority margin of 6 points, a SD of 19.2, a power of 80% and an alpha level of 5% results in a total sample size of n=94 (n=47 in each group). After allowing a dropout-rate of up to 28% our required sample size will be n=120 (n=60 in each group).

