## **Randomization**

After baseline assessment, patients will be randomly assigned to either a supervised strength exercise intervention or usual care with a 1:1 allocation as per a computer-generated randomization schedule, stratified by hospital site (Aarhus, Odense, Aalborg, Horsens, Hvidovre, or Melbourne).

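### The primary mixed model leaves baseline iHOT-33 means free to differ by arm, so the 6-month contrast is the unadjusted difference in change: valid, but usually less precise than the collected data allow

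*SAP*

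**What the plan says.** The SAP's Primary outcome section defines the endpoint as change in iHOT-33 from baseline to 6 months. Under Intention-to-treat analysis, the model is described as follows: "The model will include fixed effects for the intervention group (physiotherapist-led exercise or usual care) and time points (Baseline, 3, 6, and 12 months"), and "an interaction term between the intervention group and time will be included". Nothing in the SAP sets the two baseline means equal or enters baseline iHOT-33 as a covariate. The decision rule is that "the lower limit of the 95% confidence interval for the mean difference must be greater than 6.1 points".

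On correlation and clustering: "Patients and recruitment sites (Aarhus, Aalborg, Hvidovre, Horsens, or Melbourne) will be included as random effects to account for potential clustering effects". No within-patient covariance structure is named. Model validation includes "comparing observed and expected within-subject standard deviations and correlations", with no action stated if they disagree.

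The site list in that sentence has five names. Trial design has the study "conducted in Denmark (Aarhus, Horsens, Hvidovre, Aalborg, and Odense) and Australia (Melbourne"), and Randomization is "stratified by hospital site (Aarhus, Odense, Aalborg, Horsens, Hvidovre, or Melbourne"). Both of these include Odense, which makes six.

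**The concern.** A free group effect, four time levels and their interaction give eight unrestricted means, two of them at baseline. The 6-month effect then subtracts the observed baseline difference in full. In a randomised trial that difference is pure chance, and subtracting all of it is optimal only in a special case (step 3 of the working). Otherwise the interval is wider than it needs to be, and under the 6.1 rule its width decides whether an observed benefit counts as effectiveness.

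Two smaller matters sit in the same lines.

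- Read plainly, patient as a random effect is a random intercept, which assumes one variance and one correlation for all visits. If that is wrong, the standard error is wrong, and the SAP leaves open what would then be done.
- The five-site list contradicts the six randomisation strata. This is a slip in a list and costs no precision.

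**Working it through.** **Inputs.** From Sample size calculation: true difference 16, SD of change 19.2, 47 per arm. From Intention-to-treat analysis: margin 6.1, two-sided 95% interval. Assumed, because the SAP gives neither: r, the baseline-to-6-month correlation, and k, the baseline SD divided by the 6-month SD.

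**1. The plan's own figures.** √((26² + 8²)/2) = 19.24, so 19.2 is the pooled pilot SD of change, with no baseline adjustment. A net difference of 16 − 6 = 10 with SD 19.2 and 80% power gives 46 per arm by the normal formula and 47 by the t distribution at one-sided 5%. This reproduces 47 per arm and 94 in total. Two-sided 5% gives 58 or 59.

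**2. The planned model.** In 150 simulated complete-data trials, the 6-month interaction coefficient equalled the raw difference in mean change (largest gap 3 × 10⁻¹³).
- Standard error: 19.2 × √(2/47) = 3.96.
- Half-width: 1.986 × 3.96 = 7.87.
- Smallest observed difference that passes: 6.1 + 7.87 = 13.97.
- Power (noncentral t, excess 16 − 6.1 = 9.9, one-sided 2.5%): 69.6%.

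**3. A common baseline mean.** With 6-month SD σ, the per-patient variance is σ²(1 + k² − 2rk) for raw change and σ²(1 − r²) after optimal use of baseline. The ratio is (1 − r²)/(1 + k² − 2rk). The denominator exceeds the numerator by (k − r)², so in large samples the ratio never exceeds 1, and equals 1 only if k = r. For k = 1 it is (1 + r)/2.

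| r (k = 1) | Variance ratio | Effective SD | Half-width | Smallest passing difference | Power | Implied raw SD |
|---|---|---|---|---|---|---|
| 0.3 | 0.65 | 15.5 | 6.34 | 12.4 | 86.6% | 16.2 |
| 0.5 | 0.75 | 16.6 | 6.81 | 12.9 | 81.5% | 19.2 |
| 0.7 | 0.85 | 17.7 | 7.25 | 13.4 | 76.5% | 24.8 |
| 0.8 | 0.90 | 18.2 | 7.46 | 13.6 | 74.1% | 30.4 |

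The last column is 19.2/√(2(1 − r)), the raw SD implied by holding the SD of change at 19.2.

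**4. Unequal SDs.** Power at 47 per arm, against 69.6% unadjusted:

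| k | r = 0.3 | 0.5 | 0.7 | 0.8 |
|---|---|---|---|---|
| 0.7 | 76.5% | 71.9% | 69.6% | 70.8% |
| 0.8 | 79.7% | 74.5% | 70.5% | 69.6% |
| 1.25 | 93.7% | 90.5% | 87.7% | 87.1% |

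**5. Checks.**
- Simulation (40,000 complete-data trials per setting, k = 1, slope estimated): adjusted power 86.1%, 80.7%, 75.9% and 73.9%, against 69.3–69.9% unadjusted.
- One-sided error at a true difference of 6.1 was 2.4–2.7% for both analyses.
- With an assumed dropout pattern (60 enrolled and 47 seen at 6 months per arm), the variance ratios are 0.70, 0.79 and 0.88 at r = 0.3, 0.5 and 0.7.

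**6. Covariance.** Suppose a random intercept is fitted to visits at 0, 3, 6 and 12 months. Its standard error for the 6-month change, divided by the true one, gives a one-sided error of 1 − Φ(1.96 × ratio).

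| True pattern | SE ratio | One-sided error |
|---|---|---|
| All correlations 0.5 | 1.000 | 2.5% |
| Decay 0.7–0.9 per 3 months | 0.996–1.024 | 2.2–2.5% |
| Correlations 0.5, baseline SD 0.9–0.7 of the others | 1.024–1.064 | 1.9–2.2% |
| 0.5 with baseline, 0.65 among follow-ups | 0.922 | 3.5% |
| 0.5 with baseline, 0.75 among follow-ups | 0.866 | 4.5% |

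**The case against.** The planned analysis is valid and consistent with itself: the endpoint, the contrast and the planning SD all concern change. On that view this is a preference, not an error.

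The 70% starting power is also not the model's doing. It comes mainly from sizing at one-sided 5% while deciding on a 95% interval. With all 60 per arm analysed, the unadjusted rule reaches 80%.

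The gain is not anchored in the documents either. No single r in the range fits the pilot: with a raw SD of 16 at both visits, a change SD of 26 needs r = −0.32 and one of 8 needs r = 0.88. The large spread of change in the exercise arm may mean that scores fan out after treatment (k below 1), which shrinks the gain. Finally, an unstructured covariance over four visits has 10 parameters against 2, and the full proposed model with sites and dropout was not simulated.

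Much of this stands. The plan is not biased on this point, the size of the gain is uncertain, and the sample-size mismatch is a separate matter. It does not remove the case for change. In large samples the adjusted contrast is never less precise. Full retention is not what the plan expects, and at 60 per arm with k = 1 power would still rise from 80.0% to 93.5%, 89.9%, 86.0% or 84.0% at the four values of r. Ten covariance parameters are manageable at this sample size if a fallback is named.

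**Conclusion.** The point holds as a loss of precision, not as bias. The change should be made. At 47 per arm with equal visit SDs and r from 0.3 to 0.8, the variance is 35% to 10% larger than it need be, taken as a share of the planned variance. Observed differences from 12.4–13.6 up to 14.0 would fail under the planned model and could pass under the better one.

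This rests on an SD of change of 19.2, a true difference of 16, and assumed values of r and k. If the baseline SD is clearly below the 6-month SD and r is high, little or nothing is gained.

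The covariance point is secondary. A plain random intercept could leave the interval slightly too wide or too narrow, and the direction cannot be known beforehand. The missing site is an inconsistency to correct, with no numerical consequence.

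**What to change.** Rewrite the model lines in Intention-to-treat analysis before unblinded data are seen:

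- Constrain the arms to a common baseline mean: fixed effects for time and for group at each post-baseline visit, with no group effect at baseline. Alternatively, model the 3-, 6- and 12-month scores with group-by-time, baseline iHOT-33 and baseline-by-time terms.
- State an unstructured within-patient covariance over the modelled visits in place of the patient random intercept, and name the fallback structure if the model does not converge.
- Keep site in the model as planned, but list all six randomisation sites, including Odense.
- Report the month-6 contrast with its 95% interval against 6.1.

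The estimand stays the same: when the true baseline means are equal, the difference in change and the difference at 6 months coincide. The cost is a few lines of SAP text and Stata code, with no new data or patients. The downside is the larger number of covariance parameters.

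### The primary mixed model names no residual covariance; on its plain reading the interval compared with 6.1 can have the wrong width, and the planned check has no stated consequence

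*SAP*

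**What the plan says.** The SAP, under Primary analysis (Intention-to-treat analysis), analyses continuous outcomes with a linear mixed model. Its fixed effects are group, visit (baseline, 3, 6 and 12 months) and their interaction. On the random part it says: "Patients and recruitment sites (Aarhus, Aalborg, Hvidovre, Horsens, or Melbourne) will be included as random effects to account for potential clustering effects". (Odense, a stratum in the Randomization section, is missing from that list; this is a separate matter.) The model is justified thus: "This approach accounts for the correlation between repeated measurements within the same patient over time". No random slope, residual covariance structure, robust variance or degrees-of-freedom method is named.

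The trial is decided by one interval from this model: "the lower limit of the 95% confidence interval for the mean difference must be greater than 6.1 points".

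The same section plans a diagnostic: "Model validation will be performed by comparing observed and expected within-subject standard deviations and correlations", along with residual and QQ plots. It does not say what follows if observed and expected values disagree.

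The only variability figures are in the Sample size calculation, from a 12-week pilot: "mean change of 27 (SD 26) points on the iHOT-33 in their strength exercise group" and "a mean change of 11 (SD 8) points in their stretching group". These are SDs of change. The SAP gives no SD at any single visit and no correlation between visits.

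**The concern.** A patient random effect with independent residuals does account for within-patient correlation, but in one pattern only: one variance at every visit and one correlation for every pair of visits. Under it, the standard errors of the 3-, 6- and 12-month differences in change are identical with complete data, whatever the data show. If the true pattern differs, the standard error of the 6-month contrast is too small or too large.

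Success depends only on the lower confidence limit, so the error passes straight into the primary conclusion. The plan assumes "The estimated mean difference of 16 points", which is 16 − 6.1 = 9.9 points above the threshold. Against that distance, a half-width that is wrong by up to about 1.4 points matters.

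The second route is missing data. The SAP allows for dropout of up to 28%, links dropout to insufficient improvement (Dropouts) and imputes nothing in the primary analysis (Missing data). The model's correlations then decide how observed visits inform missing 6-month scores. If those correlations are wrong, some bias can remain even under missing at random.

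**Working it through.** **The plan's own figures.** Pooling the pilot SDs gives √((26² + 8²)/2) = √370 = 19.24, matching the stated 19.2. With a distance of 16 − 6 = 10, n per arm = 2(1.645 + 0.842)² × 19.2²/10² = 45.6, so 46, or 47 with the t correction. This matches the stated 47, using one-sided 5%. Sidedness is a separate matter; 47 per arm is used below as the number of completers.

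**Formula.** Take a random-intercept model with free group-by-visit means and complete data. The variance of the 6-month difference in change is 2σ²ₑ(1/n₁ + 1/n₂). The model estimates 2σ²ₑ as the mean of Var(Yⱼ − Yₖ) over the six visit pairs. The true variance uses Var(Y₆ − Y₀) alone. Hence

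r = reported SE / true SE = √[mean over six pairs of Var(Yⱼ − Yₖ) / Var(Y₆ − Y₀)].

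Coverage = 2Φ(1.96r) − 1. False success at a true difference of 6.1 = 1 − Φ(1.96r).

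**True half-width.** With SD of change 19.2 and 47 per arm: 1.96 × 19.2 × √(2/47) = 7.76 points.

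**One case in full (assumed correlations).** Let the visit SDs be equal, the correlation with baseline 0.5 and the correlation among follow-ups 0.8. In units of the visit variance, each of the three baseline pairs has 2(1 − 0.5) = 1.0 and each of the three follow-up pairs has 2(1 − 0.8) = 0.4. The mean is 0.70, so r = √(0.70/1.00) = 0.837. The half-width is 0.837 × 7.76 = 6.49, coverage 89.9% and false success 5.1%. A simulation of 20,000 trials at 47 per arm gave coverage 90.3%, mean half-width 6.49 and false success 4.8%.

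**Range (all patterns assumed; SD of the 0–6 month change fixed at 19.2).**

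| Pattern | r | Half-width | Coverage | False success |
|---|---|---|---|---|
| Equal variances and correlations | 1.00 | 7.76 | 95.0% | 2.5% |
| Correlation decaying, 0.7–0.9 per 3 months | 1.00–1.02 | 7.73–7.95 | 94.9–95.5% | 2.5–2.2% |
| Follow-up SD 1.2–1.4 × baseline, equal correlation | 1.03–1.06 | 8.02–8.25 | 95.7–96.3% | 2.1–1.9% |
| SDs in ratio 1, 1.1, 1.2, 1.4; correlation 0.8 per 3 months | 1.10 | 8.53 | 96.9% | 1.6% |
| Correlation 0.4–0.5 with baseline, 0.6–0.8 among follow-ups | 0.82–0.95 | 6.34–7.40 | 89.0–93.8% | 5.5–3.1% |

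The ends of the last row are:
- Correlations 0.4 and 0.8, equal SDs: √[((1.2 + 0.4)/2)/1.2] = 0.816.
- Correlations 0.4 and 0.6, follow-up SD 1.3 × baseline: baseline pairs 1 + 1.69 − 2(0.4)(1.3) = 1.65, follow-up pairs 2(1.69)(0.4) = 1.352, so √(1.501/1.65) = 0.954.

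**Unequal arm SDs.** With 47 per arm, the pooled SE is √(370 × 2/47) = 3.97 and the arm-specific SE is √(676/47 + 64/47) = 3.97, which is identical. With 40 exercise and 54 control completers, the pooled variance is (39 × 676 + 53 × 64)/92 = 323.4. The pooled SE is then 3.75 against a true 4.25, ratio 0.88. With 51 and 43 it is 4.12 against 3.84, ratio 1.07.

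**Dropout.** One check assumed correlations of 0.5 and 0.8 as above, with dropout of 18% and 26% in the two arms driven by the 3-month score. The equal-correlation model overstated change by 1.1 to 1.5 points in each arm and moved the between-arm difference by about −0.4. The correct covariance gave essentially no bias. The size depends on how strongly dropout follows the score.

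**The case against.** The SAP never says intercept, independent residuals or compound symmetry, so a richer residual structure is not excluded. That is right, and the point should not be put as though the SAP had expressly chosen a single random intercept. But if the wording is open, the standard error of the deciding interval is not pre-specified, and the remedy is the same.

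A reader might infer that the interval is certain to be too narrow. The documents do not support this. They give no visit correlations, and over the assumed patterns the interval is about right, too wide or too narrow. With complete data the 6-month estimate itself does not depend on the covariance choice.

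A reader might also take the pilot SDs of 26 and 8 as proof that the model misstates the width. They are not: with equal completers the pooled and separate standard errors coincide. Simulated coverage with these SDs and equal correlations was 94.9%. They also come from 12 weeks and a stretching control, not 6 months of usual care.

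Finally, the SAP does plan the relevant diagnostic. That counts in its favour, but with no stated consequence any remedy would be chosen after seeing the data. The objection that separate matrices by arm would be heavy (20 parameters, about 47 completers per arm) also stands, so a common matrix is the better default.

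**Conclusion.** The point holds in limited form and should be fixed. The covariance structure of the model that decides the trial is not stated. Its plain reading imposes equal variances and correlations over visits, and the planned check leads nowhere.

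The consequence is conditional on assumed visit patterns, 47 completers per arm and complete data: a standard-error ratio from 0.82 to 1.10 and coverage from 89 to 97%. In the unfavourable pattern, where follow-ups correlate more with each other than with baseline, false success at the margin is 3.1 to 5.5% instead of 2.5%. Unequal arm variances matter for the width only if completer numbers differ between arms. Bias through dropout is possible under missing at random; in the one case checked it was a few tenths of a point in the between-arm difference.

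**What to change.** For continuous outcomes, replace the patient random intercept with an unstructured residual covariance over visits, common to both arms. Fit it by REML with Kenward-Roger degrees of freedom and keep the site term. Take the 6-month contrast and its 95% interval from this model.

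State what follows from the planned check. An arm-specific covariance can be a sensitivity analysis, or be used if the check shows clearly different arm variances.

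Pre-specify the fallback for non-convergence: a random intercept with patient-clustered robust standard errors. In that fallback site is best entered as a fixed effect, because clustering on patient treats patients as independent.

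The change bites for outcomes with four visits. The performance tests have only baseline and 6 months, hence a single visit pair, and with complete data the averaging problem does not arise there.

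Cost: a few lines of SAP text and one model option before unblinding. Four visits need 4 variances and 6 covariances, 10 parameters in place of 2, with some risk of non-convergence that the fallback covers.
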